8.2.12.2. PHQ-9

The PHQ-9 questionnaire is a validated, participant-completed 9-item depression module of the Patient Health Questionnaire, which is used as a diagnostic instrument for common mental

disorders. The PHQ-9 consists of 9 items each scored on a scale of 0 = “not at all” to 3 = “nearly every day” with a recall period of “the last 2 weeks.” Major depression is diagnosed if 5 or more of the 9 depressive symptom criteria have been present at least “more than half the days” in the past 2 weeks, and 1 of the symptoms is depressed mood or anhedonia. As a severity measure, a higher score indicates greater severity (Kroenke et al. 2001).

Participants will be referred to a Mental Health Professional if in the opinion of the investigator it is necessary for the safety of the participant or if at any time the participant has a PHQ-9 score ≥ 15 .

8.2.13. Additional Safety Data and Sample Collections

For some interventions, additional data or sample collections may be necessary when certain AEs occur. See the ISAs for any additional data or sample collections for such AEs and additional instructions, if applicable.

8.3. Adverse Events, Serious Adverse Events, and Product Complaints

The definitions of the following events can be found in Section 10.3:

- AEs
- SAEs, and
- Product complaints (PCs).

These events will be reported by the participant (or, when appropriate, by a caregiver, surrogate, or the participant’s legally authorized representative).

The investigator and any qualified designees are responsible for detecting, documenting, and recording events that meet these definitions and remain responsible for following up events that are serious, considered related to the study intervention or study procedures, or that caused the participant to discontinue the study intervention or the study (see Section 7).

Care will be taken not to introduce bias when detecting events. Open-ended and non-leading verbal questioning of the participant is the preferred method to inquire about event occurrences.

After the initial report, the investigator is required to proactively follow each participant at subsequent visits or contacts. All SAEs and AEs of special interest (as defined in the ISAs) will be followed until resolution, stabilization, the event is otherwise explained, or the participant is lost to follow-up (as defined in Section 7.3). For PCs, the investigator is responsible for ensuring that follow-up includes any supplemental investigations as indicated to elucidate the nature and/or causality. Further information on follow-up procedures is provided in Section 10.3.

8.3.1. Timing and Mechanism for Collecting Events

This table describes the timing, deadlines, and mechanism for collecting events.

Event	Collection Start	Collection Stop	Timing for Reporting to Sponsor or Designee	Mechanism for Reporting	Back-up Method of Reporting
Adverse Event					
AE-related to prescreening study procedure	Signing of the pre-screening ICF	Participation in the study has ended	As soon as possible upon site awareness	AE CRF	N/A
AE	Signing of the ICF	Participation in the study has ended	As soon as possible upon site awareness	AE CRF	N/A
Serious Adverse Event					
SAE and SAE updates – prior to start of study intervention and deemed reasonably possibly related to study procedures	Signing of the ICF	Start of intervention	Within 24 hours of awareness	SAE CRF	SAE paper form
SAE and SAE updates – after start of study intervention	Start of intervention	Participation in study has ended	Within 24 hours of awareness	SAE CRF	SAE paper form
SAE ^a – after participant's study participation has ended and the investigator becomes aware	After participant's study participation has ended	N/A	Promptly	SAE paper form	N/A

Event	Collection Start	Collection Stop	Timing for Reporting to Sponsor or Designee	Mechanism for Reporting	Back-up Method of Reporting
Pregnancy					
Pregnancy in female participants and female partners of male participants	After the start of study intervention	At least 5 half-lives plus 30 days (female partners of male participants) and 5 half-lives plus 30 days (female participants) after the last dose or, until study participation has ended, whichever is later.	Within 24 hours (see Section 8.3.2)	Pregnancy paper form	Pregnancy paper form
Product Complaints					
PC associated with an SAE or might have led to an SAE	Start of study intervention	End of study intervention	Within 24 hours of awareness	Product Complaint Form	N/A
PC not associated with an SAE	Start of study intervention	End of study intervention	Within 1 business day of awareness	Product Complaint Form	N/A
Updated PC information	—	—	As soon as possible upon site awareness	Originally completed Product Complaint Form with all changes signed and dated by the investigator	N/A
PC (if investigator becomes aware)	Participation in study has ended	N/A	Promptly	Product Complaint Form	

^a SAEs should not be reported unless the investigator deems them to be possibly related to study treatment or study participation.

8.3.1.1. Adverse Event Monitoring with a Systematic Questionnaire

Nonleading AE collection should occur prior to the collection of the C-SSRS.

If a suicide-related event is discovered *during the C-SSRS* but was not captured during the nonleading AE collection, sites should not change the AE form.

If an AE is serious or leads to discontinuation, it needs to be included on the AE form and the process for reporting SAEs is followed.

8.3.2. Pregnancy

Collection of pregnancy information

Male participants with partners who become pregnant

- The investigator will attempt to collect pregnancy information on any male participant's female partner who becomes pregnant while the male participant is in this study. This applies only to male participants who receive study intervention.
- After learning of a pregnancy in the female partner of a study participant, the investigator
 - will obtain a consent to release information from the pregnant female partner directly, and
 - within 24 hours after obtaining this consent, will record pregnancy information on the appropriate form and submit it to the sponsor.

The female partner will also be followed to determine the outcome of the pregnancy. Information on the status of the mother and child will be forwarded to the sponsor. Generally, the follow-up will be no longer than 6 to 8 weeks following the estimated delivery date. Any termination of the pregnancy will be reported regardless of gestational age, fetal status (presence or absence of anomalies), or indication for the procedure.

Female participants who become pregnant

The investigator will collect pregnancy information on any female participant who becomes pregnant while participating in this study. The initial information will be recorded on the appropriate form and submitted to the sponsor within 24 hours of learning of a participant's pregnancy.

The participant will be followed to determine the outcome of the pregnancy. The investigator will collect follow-up information on the participant and the neonate and the information will be forwarded to the sponsor. Generally, follow-up will not be required for longer than 6 to 8 weeks beyond the estimated delivery date. Any termination of pregnancy will be reported, regardless of gestational age, fetal status (presence or absence of anomalies), or indication for the procedure.

While pregnancy itself is not considered to be an AE or SAE, any pregnancy complication or elective termination of a pregnancy for medical reasons will be reported as an AE or SAE.

A spontaneous abortion (occurring at <20 weeks gestational age) or still birth (occurring at ≥20 weeks gestational age) is always considered to be an SAE and will be reported as such.

Any poststudy pregnancy-related SAE considered reasonably related to the study intervention by the investigator will be reported to the sponsor as described in protocol Section 8.3.1. While the investigator is not obligated to actively seek this information in former study participants, he or she may learn of an SAE through spontaneous reporting.

Any female participant who becomes pregnant while participating in the study will discontinue study intervention. If the participant is discontinued from the study, follow the standard discontinuation process and continue directly to the follow-up phase. The follow-up on the pregnancy outcome should continue independent of intervention or study discontinuation.

8.3.3. Adverse Events of Special Interest

See the relevant ISA.

8.4. Pharmacokinetics

See the relevant ISA.

Sample retention is described in Section 10.1.12.

8.5. Pharmacodynamics

See the relevant ISA.

Sample retention is described in Section 10.1.12.

8.6. Genetics

See the relevant ISA.

Sample retention is described in Section 10.1.12.

8.7. Biomarkers

See the relevant ISA.

Sample retention is described in Section 10.1.12.

8.8. Immunogenicity Assessments

Immunogenicity may be evaluated in the ISAs governed by this protocol. Information on immunogenicity sample collection and assessment will be described in the ISA as applicable.

Refer to Section 10.1.12, Appendix 1 for details on sample retention.

8.9. Health Economics OR Medical Resource Utilization and Health Economics

If applicable, see the relevant ISA.

9. Statistical Considerations

The statistical analysis plan (SAP) for the CWMM master protocol and each respective ISA will include a more technical and detailed description of the statistical analyses described in this section. This section is a summary of the planned statistical analyses of the common endpoints shared across all the ISAs.

9.1. Statistical Hypotheses

For each ISA of the CWMM master protocol, the primary null hypothesis is that there is no difference between the intervention and primary control on the primary endpoint and time point. The null hypothesis for secondary objectives is that there is no difference between the intervention and primary control for secondary endpoints at time points of interest. Intervention-specific details regarding hypotheses and statistical testing will be detailed in the respective ISAs.

9.1.1. Multiplicity Adjustment

No adjustments or control for multiplicity will be performed unless specified in the ISA SAP.

9.2. Analysis Sets

This table describes the populations and data points that will be used for statistical analyses within each ISA of the CWMM master protocol. Additional intervention-specific populations for analyses may be described in the ISAs:

Participant Analysis Set	Description
Full analysis set (FAS)	All randomized participants who meet the inclusion criteria.
Safety analysis set (SAS)	All participants who are exposed to investigational intervention.

The following data point sets are defined:

Data Point Sets	Description
DPS1	Data points obtained during treatment period at or after randomization up to the date of discontinuation of any study drug or intercurrent events (ICEs) specified in respective ISAs.
DPS2	Data points obtained during treatment period at or after randomization regardless of adherence to study drug.
DPS3	Data points obtained during treatment period plus safety follow-up period regardless of adherence to study drug.

Abbreviation: DPS = data point set.

FAS and DPS1 will be used to estimate the primary estimand (efficacy estimand) for primary and secondary objectives.

FAS and DPS2 may be used to estimate the additional estimands for the primary and secondary objectives.

SAS and DPS3 will be used to present safety data.

For the efficacy analyses, participants will be included in the analyses according to the planned investigational intervention; whereas for safety analyses, participants will be included in the analyses according to the investigational intervention they actually received.

9.3. Statistical Analyses

9.3.1. General Considerations

Statistical analyses of the CWMM master protocol and ISAs will be the responsibility of the sponsor or its designee. Multiple SAPs will be defined and used throughout the duration of the entire CWMM master protocol. A single CWMM master protocol SAP will be developed, as well as an ISA SAP, for each ISA. The CWMM master protocol SAP describes the statistical analyses that are common across the entire CWMM master protocol, and the analyses will be conducted within each ISA. The analyses in the CWMM master protocol SAP will include

- disposition reports
- AE analyses
- laboratory analyses
- vital signs analyses
- PK parameters analyses, and
- efficacy analyses that do not depend on borrowing of comparator and primary control information from other ISAs.

The ISA SAP will contain the statistical analyses unique for each ISA and may include

- the proposed strategy of borrowing comparator and primary control information from other ISAs
- if any partial borrowing of placebo information is implemented, the model used for the primary and secondary analyses, and
- details of analyses that are unique to the ISA or analyses that may differ from what is specified in the CWMM master protocol SAP.

If there is a discrepancy between the CWMM master protocol SAP and the ISA SAP, the methodology in the ISA SAP will be used.

Changes to the CWMM master protocol data analyses methods will require an amendment only if they change a principal feature of the master protocol. Any other change to the data analyses methods, and the justification for making the change, will be described in the SAP and the clinical study report for each respective ISA.

The initial ISA will not have an opportunity to prospectively borrow control information from other ISAs; borrowing control information may occur in subsequent ISA analyses when appropriate. Bayesian hierarchical modeling and other modeling approaches will be considered for borrowing information. Analysis details and impact on sample size will be provided in the ISA and its respective SAP.

The CWMM master protocol SAP will be finalized prior to the unblinding of the first ISA. The ISA SAP will be finalized prior to the first unblinding of the respective ISA.

The specific baseline definitions for each analysis will be provided in the CWMM master protocol SAP.

All tests of treatment effects will be conducted at a 2-sided alpha level of **CC1**, unless otherwise stated, and all confidence intervals will be given at a 2-sided **CC**% level. Unless otherwise stated in an ISA, the primary estimand of interest in comparing efficacy of primary intervention doses with the primary control is the “efficacy” estimand, which represents the effect of treatment in the hypothetical scenario where the patient did not discontinue study drug. The primary efficacy assessment, guided by the “efficacy” estimand, will be conducted using the FAS and DPS1 dataset (see Analyses Sets table in Section 9.2). For the efficacy estimand, the hypothetical strategy is used to handle the ICEs (permanent discontinuation of study drug), so only data collected before the occurrence of any ICEs will be used in the mixed model for repeated measures (MMRM) analysis (Section 9.3.1). Efficacy measures will be implicitly imputed for visits occurring after the ICEs.

The summary statistics for continuous measures will include sample size, mean, standard deviation, median, minimum, and maximum. Unless stated otherwise in an ISA's SAP, the analysis model to make comparisons among treatment groups relative to continuous measurements assessed over time, in addition to the baseline and end of treatment measurements, will be an MMRM. Analysis of Heterogeneous Covariance (ANHECOVA) (Ye et al. 2022) may be used to make comparisons among treatment groups for continuous measurements with only 1 postbaseline assessment.

Summary statistics for categorical measures, including categorized continuous measures, will include sample size, frequency, and percentages. Fisher's exact test will be used to examine the treatment difference in categorical outcomes.

Logistic regression may be used to examine the treatment difference in binary efficacy outcomes. The negative binomial regression model may be used for the treatment comparison of discrete count measures if deemed appropriate.

9.3.2. Primary Endpoint Analysis

The primary efficacy assessment, guided by the "efficacy estimand," will be conducted using the FAS and DPS1 dataset for the primary endpoint (percent change from baseline in body weight at the primary time point).

The primary efficacy comparison will be based on the contrast between each treatment group (group of cohorts with the same target dose) of primary intervention and primary control at the ISA-specified primary time point from the MMRM analysis of percent change from baseline in body weight using the FAS and DPS1 dataset (Section 9.2). The analysis model and selection of covariance structure will be described in each ISA.

Treatment comparisons will be performed for the primary objective at the full significance level of CCI

9.3.3. Secondary Endpoint(s) Analysis

9.3.3.1. Efficacy Analyses

The following secondary endpoints will be analyzed on the FAS and DPS1 dataset:

- mean change from baseline in body weight (kg) from randomization at the primary time point
- incidence of study participants who achieve the following criteria from randomization at the primary time point:
 - $\geq 5\%$ body weight reduction
 - $\geq 10\%$ body weight reduction, and
- mean change in BMI (kg/m^2) from randomization at the primary time point.

Analyses of continuous endpoints, including change in body weight (kg), BMI (kg/m^2), will be conducted in a manner similar to the primary efficacy analyses discussed in Section 9.3.2.

Analyses for incidence of participants reaching $\geq 5\%$ body weight reduction and $\geq 10\%$ body weight reduction from baseline at the ISA-specified primary time point will be conducted using a

longitudinal logistic regression analysis. The analysis model, covariates, and selection of covariance structure will be described in the CWMM master protocol SAP and each ISA's SAP. Additional secondary efficacy analyses may be performed, if deemed necessary and specified in master and/or the respective ISA SAP.

9.3.4. Exploratory Endpoint(s) Analysis

Details of the analyses will be provided in the CWMM master protocol SAP as well as each ISA SAP.

9.3.5. Safety Analyses

All safety analyses will be conducted on the safety analysis set and DPS3 (Section 9.2) for each ISA. Safety assessments will be guided by an estimand comparing safety of primary intervention to the primary control irrespective of adherence to study drug.

For each ISA, AEs will be coded from the actual term using the Medical Dictionary for Regulatory Activities (MedDRA) and reported with preferred terms and system organ class. Summary statistics will be provided for incidence of TEAEs, SAEs, study discontinuation due to AEs, study drug discontinuation due to AEs, deaths, and other CV endpoints. Counts and proportions of participants experiencing AEs will be reported for each treatment group and each dose escalation subgroup, and Fisher's exact test will be used to compare the primary intervention dose groups with the primary control.

9.3.5.1. Central Laboratory Measures, Vitals and Electrocardiograms

Values and change from baseline to postbaseline values of central laboratory measures, vital signs, and selected ECG parameters will be summarized for each treatment group at each scheduled visit. The details will be provided in the respective ISA SAP.

9.3.5.2. Analysis of C-SSRS Data

Suicide-related thoughts and behaviors occurring during treatment will be summarized based on responses to the C-SSRS consistent with the C-SSRS Scoring and Data Analysis Guide (C-SSRS WWW).

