- change in body weight (kg) from baseline at the primary time point
- incidence of study participants who achieve $\geq 5\%$ body weight reduction at the primary time point
- incidence of study participants who achieve $\geq 10\%$ body weight reduction at the primary time point, and
- change in body mass index (BMI) (kg/m^2) from baseline at the primary time point Unless specified otherwise, safety and tolerability assessments will be guided by an estimand comparing the primary intervention doses with primary control irrespective of adherence to study drug, including data collected during the treatment period plus safety follow-up from participants who are randomly assigned and are exposed to at least 1 dose of study drug.

4. Study Design

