Confirm the participant meets applicable eligibility criteria before proceeding to Visit 401. It is recommended that the prescreening visit be performed within 4 weeks of Visit 401. Certain activities will be repeated at Visit 401 for confirmation of study eligibility, including collection of height and weight to calculate BMI and HbA1c measurement via the central laboratory.

Screening (Visit 401)

The screening period of the CWMM master protocol and ISAs may begin approximately 4 weeks before a participant receives study intervention in an ISA. All screening procedures for the CWMM master and relevant ISAs will be completed during Visit 401. Sections 5.1 and 5.2

of the CWMM master protocol provide the criteria by which participants will be screened for inclusion in, or exclusion from, the master protocol. Sections 5.1 and 5.2 of the relevant ISAs provide ISA-specific eligibility criteria.

If the time between Visit 401 and randomization (Visit 0) takes more or less time than █ weeks, it will not be considered a protocol deviation for any ISA. However, if this interval is greater than █ weeks, the participant should be rescreened.

Participants who have not fasted for Visit 401 will need to return to the site for collection of fasting parameters. This return visit will be considered part of Visit 401.

Randomization to ISAs

Participants found eligible according to all CWMM master protocol trial entry criteria, and all entry criteria of at least 1 available ISA, will be randomized or assigned to an ISAs during Visit 401. The assignment to an ISA will not be blinded.

Treatment and posttreatment periods

The treatment period of an ISA begins at the end of the ISA-specific screening/lead-in period and starts with randomization to a treatment group. The duration of the treatment period may vary across ISAs. Participants will be randomly assigned to a treatment arm within an ISA at Visit 0. When the treatment period ends, participants in every ISA will have at least 1 posttreatment follow-up visit (Visit 801).

Some aspects of the treatment period are defined in this master protocol, as required features common to all studies (ISAs) performed under the master protocol/ISA structure. See the ISAs for procedures conducted during ISA-specific treatment and posttreatment study periods.

Early discontinuation of study intervention

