QTc	corrected QT interval
QTcF	corrected QT interval (Fridericia)
QTL	quality tolerance limit
SAE	serious adverse event
SAP	statistical analysis plan

screen	The act of determining if an individual meets minimum requirements to become part of a pool of potential candidates for participation in a clinical study
SoA	schedule of activities
TBL	total bilirubin
TEAE	Treatment-emergent adverse event: An untoward medical occurrence that emerges during a defined treatment period, having been absent pretreatment, or worsens relative to the pretreatment state, and does not necessarily have to have a causal relationship with this treatment
ULN	upper limit of normal

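### Section 9.3.5.2 summarises C-SSRS events during treatment only, although Section 9.3.5 puts all safety analyses on treatment plus safety follow-up and the C-SSRS is collected in follow-up

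*Protocol*

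**What the plan says.** The general rule for safety data appears three times in the protocol, each time with the same window.

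- Section 9.3.5: "All safety analyses will be conducted on the safety analysis set and DPS3". The section adds that the comparison is made whether or not participants adhere to study drug.
- Section 9.2 defines DPS3: "Data points obtained during treatment period plus safety follow-up period regardless of adherence to study drug". It then states the rule: "SAS and DPS3 will be used to present safety data".
- Section 3, on the safety estimand, uses the same window ("including data collected during the treatment period plus safety follow-up"), with an opening qualifier: "Unless specified otherwise, safety and tolerability assessments will be guided by an estimand".

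Section 9.3.5.2, a subsection of 9.3.5, gives a narrower one for the C-SSRS: "Suicide-related thoughts and behaviors occurring during treatment will be summarized based on responses to the C-SSRS".

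Two other places fix what lies outside treatment. Section 4.1.1 starts the treatment period at randomization to a treatment group and puts at least one follow-up visit, Visit 801, after that period has ended. Section 10.13.2 lists the since-last-assessed C-SSRS among the standard activities of the posttreatment follow-up, which every ISA must have.

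**The concern.** The parent section and its subsection do not prescribe the same analysis. An analyst following 9.3.5 would include C-SSRS responses from follow-up, and one following 9.3.5.2 literally would not. Both would be following the protocol.

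At stake is whether suicide-related thoughts or behaviors that arise after the treatment period appear in the one table designed to show them. Section 8.2.12 names the end of the course of treatment, along with its beginning and any dose change, as a time for close observation. Because this is a master protocol, the wording passes to every ISA. Two ISAs could settle the question differently, and their C-SSRS tables would then not be comparable.

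**Working it through.** The protocol states no figure on this point, so there is nothing to reproduce. The check is a comparison of text.

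1. **Which data set governs?** Section 9.3.5 applies the safety analysis set and DPS3 to all safety analyses and states no exception. Section 9.3.5.2 sits under it, so the rule reaches the C-SSRS.
2. **What does DPS3 contain?** By Section 9.2, treatment period plus safety follow-up regardless of adherence. Section 3 agrees.
3. **Is follow-up separate from treatment?** Yes. By Section 4.1.1, Visit 801 comes after the treatment period ends. I take the safety follow-up of Section 9.2 to be the posttreatment follow-up of Section 10.13.2; the protocol describes no other.
4. **Is the C-SSRS collected there?** Yes, as a standard activity under Section 10.13.2.
5. **What does the C-SSRS summary cover?** By Section 9.3.5.2, events during treatment. Follow-up is not mentioned.

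Applied to C-SSRS events by when they arise:

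| Event | Collected? | In DPS3? | In the summary of 9.3.5.2 as worded? |
|---|---|---|---|
| Arises in the treatment period, participant on drug | Yes | Yes | Yes |
| Arises in the treatment period, participant has stopped drug but stays in the study | Yes, at the C-SSRS visits the participant attends | Yes | Unclear |
| Arises in follow-up, recorded at Visit 801 | Yes | Yes | No |

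The third row is the conflict. The second is only an ambiguity.

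The form used at Visit 801 asks about the time since the last assessment, so a positive answer there may relate to the last part of treatment. The literal exclusion applies to events that arise in follow-up, not to every positive response recorded at that visit.

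For contrast, SAEs, deaths and AEs leading to discontinuation have no narrower window stated anywhere, so DPS3 applies to them without conflict.

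**The case against.** The strongest reply is that this is one loose phrase. Section 8.2.12 speaks of baseline and treatment-emergent assessment of suicidality, so the words in 9.3.5.2 may only mean after baseline. The DPS2 definition shows that the protocol can speak of the treatment period while ignoring adherence. Section 3 allows departures where specified, 9.3.5.2 cites an external scoring guide, and the SAP, which is not at hand, may settle the window.

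Part of this stands. The loose reading is plausible, and the intention may well be DPS3. But 9.3.5 says all, and 9.3.5.2 does not present itself as a departure. Section 9.3.5.1, just before it, expressly leaves its details to the ISA SAP; 9.3.5.2 states a window instead. An SAP can follow only one of the two sections.

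It can also be said that nothing is lost, since AEs are collected until participation ends and SAEs have their own reporting route. That is right for the data, but less so for the tables. Section 8.3.1.1 tells sites not to change the AE form when the C-SSRS reveals a suicide-related event that open questioning had missed, unless the event is serious or leads to discontinuation. For other events the C-SSRS summary may be the only table in which they appear.

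Four stronger readings are tempting and are not supported:

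- *TEAEs are also limited to the treatment period.* The glossary in Section 10.14 reads "An untoward medical occurrence that emerges during a defined treatment period, having been absent pretreatment". It does not say which period, does not exclude follow-up and does not use the word only. Section 9.3.5 lists TEAE incidence among the analyses run on DPS3. This is an open definition of a kind commonly completed in the SAP.
- *The protocol has two safety windows throughout.* Sections 3, 9.2 and 9.3.5 give one window, and only the C-SSRS sentence departs from it.
- *Participants who stop drug early are dropped.* The wording allows that reading, but the parent section's disregard of adherence points the other way.
- *A stated share of events would be missed.* Any percentage would describe an assumed schedule, because the treatment length and the half-life multiple for follow-up are redacted.

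**Conclusion.** The point holds for the C-SSRS summary. As worded, Section 9.3.5.2 leaves out suicide-related events that arise in follow-up, although they are collected under Section 10.13.2 and fall within the data set that Section 9.3.5 requires for all safety analyses. The conclusion rests on reading treatment in 9.3.5.2 as the treatment period of Section 4.1.1, and on safety follow-up and posttreatment follow-up being the same period.

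No magnitude can be given. The primary endpoint, the sample size and the collection of safety data are unaffected; the effect is on which C-SSRS events are reported. The correction is worth making because it changes the content of a safety table at almost no cost.

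**What to change.** In Section 9.3.5.2, replace the words that limit the summary to the treatment period with: 'occurring after the first dose through the end of safety follow-up (DPS3), irrespective of adherence to study drug'. A table restricted to the treatment period can be kept as supportive. If the narrower window was intended for the main summary, the section should say that it is an exception to 9.3.5 and give the reason.

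Optionally, tie the period in the TEAE glossary entry of Section 10.14 to a named data point set. This is a clarification, not the correction of an error.

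The cost is one change of wording, with no new data or visits. The downside is that slightly more events would be reported in each arm.
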